5.3.3. Safety Endpoints

- Incidence of treatment-emergent AEs (TEAEs), particularly those of \geq CTCAE Grade 3 severity and SAEs
- Incidence of treatment-related AEs, particularly those of \geq CTCAE Grade 3 severity and SAEs
- Incidence of AEs resulting in permanent BCV or other anti-AdV drug discontinuation
- Incidence of AEs requiring BCV or other anti-AdV drug interruption
- Incidence of AEs requiring dose modification or consolidation of BCV or other anti-AdV drug
- Incidence of fatal AEs
- Incidence of and time to CTCAE Grade 2 or higher diarrhea
- Incidence of doubling, tripling, or quadrupling of baseline serum creatinine
- Incidence of need for renal replacement therapy
- Incidence of $\geq 1/2/3$ CTCAE grade increases from baseline for safety laboratory parameters of interest (by visit, maximum on-treatment, last on-treatment, last on-study)
- Distributions of change from baseline over time for central safety laboratory parameters of interest (by visit, maximum on-treatment, last on-treatment, last on-study)
- Assessment of all deaths that occur through Week 16 and in follow up through Week 36

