Serious events of diarrhea were reported by 21 subjects (10% of dosed subjects) in the CMX001-304 study. GI events were the most frequently reported AEs that led to BCV discontinuation (16% adults, 5% pediatric subjects); more specifically, diarrhea prompted BCV discontinuation in 9% adults and 5% of pediatric subjects, followed by abdominal pain (6% adults vs. < 1% pediatric subjects). Overall, more adult subjects (34%) than pediatric subjects (19%) discontinued treatment with BCV due to any AE.

Based on learnings to-date, it is recommended that BCV be interrupted for treatment-emergent diarrhea of \geq CTCAE (National Institutes of Health/National Cancer Institute Common Terminology Criteria for Adverse Events) Grade 2, with a treatment interruption of at least 7 days (i.e., at least 6 full days off drug) and until symptoms improve to \leq Grade 1. In doing so, interruption of BCV treatment serves as both a diagnostic test and, if the diarrhea is related to BCV, the time off drug also allows the gut epithelium an opportunity to regenerate. If the diarrhea improves, BCV may be safely reintroduced thereafter. A dose consolidation approach (administering the same total weekly dose at weekly dosing intervals to allow more time between doses for GI mucosal regeneration) is also recommended at re-introduction of BCV. If there is no improvement following interruption of BCV, the likely etiology of diarrhea is not BCV;

nevertheless, BCV should not be reintroduced until the diarrhea improves, regardless of the underlying etiology.

In conclusion, oral administration of BCV is associated with known GI toxicity, which cannot be reliably differentiated from GI GVHD histopathologically or based on GI symptoms. Though clinical evaluation of other organ systems also affected by GVHD, namely the skin, may assist in determining the most appropriate patient management strategy, treatment-emergent diarrhea of Grade 2 or higher severity, regardless of etiology, should prompt BCV treatment interruption for at least 7 days (i.e., 6 full days off drug). Initiation of steroid therapy for GVHD should be delayed, if clinically appropriate, in order to assess whether symptoms improve as a result of BCV withdrawal. Resumption of BCV as a consolidated QW dose is possible if symptoms improve.

Further details of this and other BCV-related toxicities are provided in the BCV Investigator's Brochure.

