4.5. Independent Safety Oversight

4.5.1. Data and Safety Monitoring Board

A DSMB will be convened according to US Food and Drug Administration (FDA) and European Medicines Agency (EMA) guidelines on clinical trial data monitoring committees to monitor safety for this study. The DSMB will review safety data on an ongoing and scheduled basis, as determined by the board and detailed in the DSMB charter. The DSMB Chair will be allowed to convene ad hoc meetings, as necessary, and meetings may be convened more frequently if unexpected safety issues arise.

The DSMB will define specific safety information to be provided for review at each meeting, but the DSMB review package will minimally include:

- All SAEs
- CTCAE Grade 3 or higher AEs
- AEs resulting in permanent BCV or other anti-AdV drug discontinuation
- AEs requiring BCV or other anti-AdV drug interruption
- AEs requiring dose modification or consolidation of BCV or other anti-AdV drug
- Incidence of and time to all-cause mortality and non-relapse mortality

- Laboratory parameters predictive of liver abnormalities (e.g., ALT, aspartate aminotransferase [AST], alkaline phosphatase, prothrombin time-international normalized ratio [PT-INR], and total and direct bilirubin), renal abnormalities (creatinine clearance, eGFR), and hematologic cell counts predictive of graft function
- Observed plasma BCV concentrations (as available)

At least two safety reviews will be conducted by the DSMB. The first safety review will be performed after the first 30 subjects enrolled into the study have completed through Week 16 (or have died or are lost to follow-up). The second safety review will be performed after the first 60 subjects enrolled have completed through Week 16 (or have died or are lost to follow-up).

The DSMB Chair will receive copies of all expedited safety reports issued for BCV at the same time these reports are submitted to investigators, and may decide to convene ad hoc DSMB meetings based on these expedited reports. If the DSMB recommends changes to the study design, including changes to the protocol dosing regimens because of safety issues, regulatory authorities will be consulted, as appropriate, prior to implementation.

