8. TREATMENT OF SUBJECTS

8.1. Administration of Standard of Care

Subjects randomized to the SoC arm in this study will be managed according to local or institutional practice guidelines and any relevant product labelling. The decisions regarding SoC, including administration of therapy, dose and regimen of therapy, modification of immunosuppression, and monitoring will be the responsibility of the clinical team according to institutional guidelines, local practices, and applicable treatment guidelines for the management of AdV infection. Investigators will need to consider the clinical status of the subjects and the local availability of treatment options.

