For subjects with CTCAE Grade 1 diarrhea or no diarrhea at baseline, BCV must be interrupted for treatment-emergent CTCAE Grade 2 or higher diarrhea. This includes new-onset Grade 2 or higher diarrhea or progression from Grade 1 to Grade 2 or higher diarrhea, regardless of the cause of the diarrhea.

In general, changing multiple therapies at the same time (e.g., interrupting BCV and starting steroids for new-onset or worsening GI GVHD) is not recommended. In order to assess response to BCV treatment interruption, start of (or increase in) steroid therapy for new-onset or worsening GI GVHD should be delayed, when possible.

- If diarrhea does not improve following ≥ 7 days interruption (at least 6 calendar days off BCV), a trial of steroid therapy for new-onset or worsening GI GVHD (while BCV is still being held) may be considered if deemed clinically appropriate.

If diarrhea does not improve to \leq CTCAE Grade 1 during interruption, BCV must not be resumed.

If diarrhea improves to \leq CTCAE Grade 1 in intensity, subjects may resume dosing of BCV, but no sooner than 7 days (i.e., at least 6 full days off drug) following the last BCV dose administration.

- If resumed, BCV must be administered in a consolidated QW dose (total weekly dose administered once weekly, i.e., 4 mg/kg, up to a maximum of 200 mg, QW in the absence of concurrent cyclosporine, or 2.8 mg/kg, up to a maximum of 140 mg, QW for subjects taking concurrent cyclosporine) to potentially improve tolerability, as weekly dosing intervals allow more time for GI mucosal regeneration between doses.

Treatment with the consolidated QW BCV dose will be continued through Week 16 post-randomization or until confirmed undetectable AdV viremia in plasma, whichever occurs first.

Recurrence of CTCAE Grade 2 or higher diarrhea after restarting BCV requires permanent discontinuation of BCV.

8.3.2.3. Treatment-emergent Diarrhea AEs in Subjects with Grade 2 or 3 Diarrhea Attributed to AdV at Baseline

For subjects with CTCAE Grade 2 or 3 diarrhea at baseline that is attributed to AdV, BCV dosing must be interrupted if:

- the diarrhea has not improved to \leq CTCAE Grade 1 after 21 days of therapy, or

- the subject experiences on-treatment worsening of one CTCAE grade or more at any time following initiation of BCV (i.e., Grade 2 worsens to \geq Grade 3, or Grade 3 worsens to \geq Grade 4), regardless of the cause of the diarrhea

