Grade 2: Increase of 4 to 6 stools per day over baseline; or moderate increase in ostomy output compared to baseline

Grade 3: Increase of \geq 7 stools per day over baseline; incontinence; hospitalization indicated; or severe increase in ostomy output compared to baseline; limiting self-care activities of daily living (ADLs)

Grade 4: Life-threatening consequences; urgent intervention indicated

Note: Action taken with BCV is regardless of the etiology of diarrhea.

Note: Pre-transplant stool output (= baseline).

Table 9: Recommended Management/Evaluation of Treatment-emergent GI Adverse Events during BCV Therapy

	Grade 1 Events	Grade 2 or Higher Events
Action with BCV	See Table 8 and Section 8.3.2	
Other interventions	
 • Avoid food/drinks that affect water transport (e.g., caffeine, alcohol, carminative spices, concentrated sugar syrups) • Avoid lactose- and sucrose-containing products • Adjust other medications associated with GI effects (e.g., macrolides, magnesium, MMF) • Symptomatic treatment dosed as needed (e.g., anti-emetics, anti-diarrheals) • Avoid starting steroid/immunosuppressants for GVHD (while dosing BCV) unless Grade 1 diarrhea persists for > 14 days 	
 • Same as for Grade 1 events • Interrupt other medications that may cause GI events (e.g., magnesium supplements, MMF) • Measure levels of immunosuppressants • Consider symptomatic treatment (e.g., anti-emetics, anti-diarrheals) dosed at regular intervals, if clinically appropriate • Fluid supplementation to maintain hydration
Other diagnostic evaluations	
 • Monitor hydration status, and supplement as needed • Evaluate for other infection • Evaluate for acute GVHD in other organ systems; consider non-GI biopsy 	
 • Same as for Grade 1 events

NOTE: When considering new-onset or worsening GI GVHD as the cause of GI symptoms:

- **Co-administration of BCV and steroids for GI GVHD is not recommended**
- In order to assess response to BCV treatment interruption, start of (or increase in) **steroid therapy for GI GVHD should be delayed, when possible**

If diarrhea does not improve following ≥ 7 days interruption (i.e., at least 6 full days off BCV), a trial of steroid therapy for new or worsening GI GVHD (while BCV is still being held) may be considered, if deemed clinically appropriate.

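### AE-driven interruption, discontinuation and dose-change counts cannot be compared between arms: the protocol mandates these actions only on BCV, and SoC subjects given no anti-AdV drug stay in the denominator

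*Combined protocol and SAP*

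**What the plan says.** Section 5.3.3 defines three endpoints by what was done with the drug: "Incidence of AEs resulting in permanent BCV or other anti-AdV drug discontinuation", "Incidence of AEs requiring BCV or other anti-AdV drug interruption" and "Incidence of AEs requiring dose modification or consolidation of BCV or other anti-AdV drug". Section 12.6.1 repeats them as AE tables, and Section 12.6 presents safety results by randomized arm. Section 4.5.1 puts the same three items in the minimum DSMB package, for example "AEs requiring dose modification or consolidation of BCV or other anti-AdV drug". Comparing overall tolerability is part of the primary objective (Section 5.1).

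For BCV, Section 8.3.2 fixes the actions:

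- **Diarrhea.** For subjects with Grade 1 or no diarrhea at baseline, "BCV must be interrupted for treatment-emergent CTCAE Grade 2 or higher diarrhea". The note to Table 8 adds: "Action taken with BCV is regardless of the etiology of diarrhea". Dosing that resumes must be consolidated to once weekly, and recurrence at Grade 2 or higher ends treatment (8.3.2.2, 8.3.2.3).
- **Non-diarrheal GI events.** Grade 3 or higher forces interruption (8.3.2.4).
- **Liver.** Five laboratory criteria force interruption, and recurrence after restart ends treatment (8.3.2.5).

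For SoC there are no protocol thresholds: subjects "will be managed according to local or institutional practice guidelines and any relevant product labelling" (Section 8.1). Section 12.6.1 allows for SoC subjects who receive no anti-AdV therapy. The safety set (Section 12.2) requires a dose on BCV but takes every subject randomized to SoC.

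**The concern.** The endpoints use one label for two different processes. On BCV, an event at a fixed grade triggers the action by rule. On SoC, a clinician decides, and some subjects have no drug to interrupt. A difference between the columns therefore mixes toxicity with the rule, the share of SoC subjects treated, and time on drug.

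The protocol itself expects some mandated interruptions for diarrhea that BCV did not cause: in Section 4.2.3.1, "interruption of BCV treatment serves as both a diagnostic test and" the absence of improvement off drug points to another cause. AE recording adds a further asymmetry. Under Section 11.9.3, a laboratory abnormality that leads to interruption of study drug becomes an AE, and the study drug described in Section 9 is BCV. The same liver values need not become an AE on SoC.

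At stake are the tolerability conclusion and what the DSMB infers. Under Section 4.3.4 the DSMB may recommend changes to subject management.

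**Working it through.** The plan gives no figure for these endpoints, so there is none to reproduce. The check asks whether equal toxicity would give equal tables and, if not, whether the direction is fixed.

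**Inputs.** From the documents: 94 BCV and 47 SoC subjects (Synopsis), and median time to clearance of 4 weeks on BCV and 9 weeks on IV cidofovir in a compassionate-use cohort (Section 4.4). Assumed, because the documents do not state them:

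- p, the risk of a threshold event, the same in both arms. I take 6%, 14% and 28%. For orientation, Section 4.2.3.1 gives 28% any-grade and 6% Grade 3 or higher diarrhea on placebo in one earlier study.
- f, the share of SoC subjects on an anti-AdV drug.
- q, the chance that an SoC clinician acts on the event.
- On BCV, action is taken as certain, which simplifies the rules.

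**Step 1: equal time on drug.** BCV action rate = p; SoC action rate = p × f × q. The last column is the exact binomial probability that the observed BCV proportion is the higher one.

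| p | f | q | BCV | SoC | P(BCV higher) |
|---|---|---|---|---|---|
| 6% | 1 | 0.5 | 6% (5.6/94) | 3.0% (1.4/47) | 0.77 |
| 14% | 1 | 0.5 | 14% (13.2/94) | 7.0% (3.3/47) | 0.89 |
| 28% | 0.7 | 0.5 | 28% (26.3/94) | 9.8% (4.6/47) | >0.99 |
| 28% | 1 | 1 | 28% (26.3/94) | 28% (13.2/47) | 0.48 |

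The contrast vanishes only when f × q = 1. The denominator alone matters: with q = 1 and f = 0.7, a 14% rate among treated SoC subjects is printed as 0.14 × 0.7 = 9.8%.

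**Step 2: unequal time on drug.** An action can occur only while drug is being given. Take an equal constant weekly hazard h = −ln(1 − p)/16. The BCV rate is 1 − exp(−4h), and the SoC event risk on drug is 1 − exp(−9h). The tables agree when f × q equals their ratio. The last column allows BCV 5 weeks, adding one week for the confirmatory sample.

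| 16-week risk p | BCV, 4 weeks | SoC drug, 9 weeks | Break-even f × q | Break-even, BCV 5 weeks |
|---|---|---|---|---|
| 14% | 3.7% | 8.1% | 0.455 | 0.566 |
| 28% | 7.9% | 16.9% | 0.467 | 0.578 |
| 40% | 12.0% | 25.0% | 0.480 | 0.591 |

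Below break-even BCV looks worse; above it SoC does. At p = 28% and 4 versus 9 weeks, f × q = 0.35 gives SoC 0.35 × 16.9 = 5.9%, below BCV's 7.9%. With f × q = 0.70, SoC is 0.70 × 16.9 = 11.8%, above it. Toxicity per week is the same in both cases.

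**Step 3: is short BCV exposure plausible?** Section 4.3.3.2 gives a median of 12 to 22 days to undetectable viremia in children, and Section 8.3.1 sets confirmation 7 to 14 days later. That is 12 + 7 = 19 to 22 + 14 = 36 days. Section 4.3.1 puts typical diarrhea onset at 4 to 6 weeks. Some episodes could therefore fall after BCV has stopped and trigger no action.

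**The case against.** The strongest reply is that these tables are descriptive and other endpoints already answer the tolerability question. Much of this stands. Section 12.6 generally plans no safety inference, and no decision rule uses the counts. Section 5.3.3 also lists Grade 2 or higher diarrhea (incidence and time), laboratory grade increases, creatinine multiples, renal replacement therapy and Grade 3 or higher AEs. Section 12.6.1 tabulates on-study AEs through Week 16, and the DSMB sees SAEs, Grade 3 or higher AEs and liver and renal laboratory data. A reader might infer that a real difference in toxicity cannot be recovered. These endpoints show that it largely can. What they lack is the composite hepatic criteria and Grade 3 or higher non-diarrheal GI events as named between-arm measures, and a statement that the comparison rests on them.

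A second reply is that interruption and consolidation are a real burden of the BCV strategy, and Section 4.3.1 calls assessment of the revised guidelines a primary objective. That is a good reason to report the counts within the BCV arm. It does not make them comparable with SoC.

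Third, the mechanism has limits. The explicit cause-blind wording concerns diarrhea, while hepatic resumption depends on finding another cause. Non-fatal AdV-related events need not be recorded as AEs (Section 11.9.1), so AdV diarrhea should not be assumed to enter the counts. Resumption is optional, so an interruption does not always produce a consolidation. SoC drugs can also be stopped under their labelling.

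**Conclusion.** The concern holds as one of comparability. Mandated actions on BCV, discretionary actions on SoC, consolidation defined only for BCV, and untreated SoC subjects in the denominator mean that the three action-based endpoints do not measure the same thing in the two arms. No planned table separates mandated from other actions.

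A reader might go further and infer that the tables will show worse tolerability on BCV even at equal toxicity, or might attach a percentage-point excess. The documents support neither. The excess follows at equal time on drug when f × q is below 1, but shorter response-driven BCV courses can offset or reverse it. In the illustration the direction turns at f × q of about 0.46 to 0.59, depending on the event risk and on whether BCV runs 4 or 5 weeks. The values of p, f and q are assumptions, and the 4 and 9 weeks come from a non-randomized cohort. The figures show that the sign is undetermined; they do not estimate a bias for this trial.

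The effect is on interpretation of the tolerability comparison and the DSMB package, not on a test or the primary efficacy result. A reporting change is worthwhile because it is cheap and specific.

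**What to change.** Leave the management rules in Section 8.3.2 unchanged. Amend Section 12.6.1 and the DSMB table specifications:

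1. State that the between-arm tolerability comparison rests on the action-independent endpoints through Week 16. Add the composite hepatic criteria of Section 8.3.2.5, derived from central laboratory values, and Grade 3 or higher non-diarrheal GI events. Apply both identically in the two arms, as analysis definitions only.
2. Present interruption, discontinuation and modification or consolidation as within-arm descriptions. Give SoC percentages over subjects who received an anti-AdV drug, show time on drug for both arms, and split BCV events into protocol-mandated versus other and related versus not related.

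The cost is SAP wording and a few more tables. Both arms follow the same assessment schedule (Section 6.2), with central laboratory tests at each visit. Relatedness and action taken are already recorded for each AE (Section 11.9.3).

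Two limits remain. The drug-treated SoC denominator is defined after randomization, so it is not a randomized comparison and should be labelled as descriptive. AE-based endpoints also still depend on open-label judgement of which events are due to AdV.

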5.3.4. Exploratory Endpoints

- Association of HCT co-morbidity index and clinical outcomes

- Change from baseline in exploratory biomarker laboratory parameters (e.g., citrulline, ST2, TIM3, and CRP)
- Association of exploratory biomarkers with treatment-emergent CTCAE Grade 2 diarrhea or GI GVHD
- Number of and reasons for emergency room (A&E) visits; number of, duration, and reasons for hospital admissions; number of days spent in ICU, in isolation, or confined to bed; other infections; receipt of and duration of relevant concomitant medications and therapies; type and number of certain diagnostic or therapeutic procedures; and provision of home healthcare through Week 16
- Association between immune reconstitution and viral response and clinical outcome (e.g., based on measurement and activity of AdV-specific cytotoxic T lymphocytes [CTLs] and other immune reconstitution parameters)

[figure not shown]
6. INVESTIGATIONAL PLAN

6.1. Overall Study Design

This is a randomized, open-label, multi-center study of the safety, overall tolerability, and antiviral activity of BCV, as compared with SoC, in pediatric recipients of a high-risk (i.e., T cell-depleted) allogeneic (i.e., non-autologous) HCT. Pediatric patients with AdV detected in plasma within the previous 21 days and for the first time since their qualifying transplant may be screened for participation in the study. Approximately 141 subjects who meet all applicable entry criteria will be randomized in a 2:1 ratio to receive either BCV or SoC. The day of randomization is defined as Day 1. Subjects randomized to receive BCV will be treated until AdV DNA is confirmed to be undetectable in plasma, up to a maximum of 16 weeks post-randomization. During randomization, subjects will be stratified based on the following variables: last (non-baseline) screening AdV viremia ($\geq 10,000$ copies/mL vs. $< 10,000$ copies/mL), time from transplant to randomization (≥ 28 days vs. < 28 days), and T cell-depletion methodology (receipt of alemtuzumab or ex vivo depletion vs. receipt of ATG). Subjects randomized to the SoC arm will be managed according to local or institutional practice guidelines for the treatment of AdV infection. All subjects, regardless of treatment assignment, will be followed in the study for a total of 36 weeks post-randomization. Subjects will be assessed on a weekly basis through Week 16, with additional assessments performed at Weeks 24 and 36 post-randomization. The data collected through Week 16 will comprise the primary data set for the study; hence, the primary database will be locked and analyzed following capture of data for all subjects through Week 16.

A schema of the overall study design is provided in Figure 9.

Figure 9: Study Design Schema for CMX001-999

Abbreviations: AUC = area under curve; BCV = brincidofovir; BIW = twice weekly.

6.2. Schedule of Assessments/Procedures

Subjects will be assessed at weekly intervals through the 16-week treatment period, with additional assessments performed at 24 and 36 weeks post-randomization as follows:

- Assessments scheduled for Weeks 1, 2, 3, 4, 6, 8, 12, and 16 must be completed in the hospital or clinic (i.e., subjects who are being treated on an outpatient basis must return to the hospital/clinic).
- For all other assessments (i.e., Weeks 5, 7, 9, 10, 11, 13, 14, 15, 24, and 36):
 - If a subject has detectable AdV in plasma, the subject will be required to return to the hospital or clinic to complete these assessments until such time as the subject achieves confirmed undetectable AdV viremia.
 - Thereafter, every effort should be made to have a subject return to the hospital or clinic for these assessments. However, if return visits to the hospital or clinic are not practical (e.g., because the subject has returned to his or her home region), these visits may be performed through a home healthcare service provider or at a third-party facility that has been pre-approved by the sponsor (for the collection of samples including blood draws for safety and/or virologic analysis). Telephone contact between the investigator and the subject or the subject's caregiver (to assess AEs, AdV symptoms, etc.) will need to occur in parallel.
 - If an approved home healthcare services provider or an approved third-party facility capable of performing the required procedures is not available, then all assessments must be performed at the hospital or clinic.

Subjects who interrupt or discontinue BCV (for any reason) will remain on the same schedule of assessments/procedures through completion of the final study assessment at Week 36. Subjects randomized to the SoC arm will follow the same schedule of assessments/procedures through Week 36 as subjects randomized to BCV with the exception of BCV dosing and PK sample collections.

Unless otherwise specified, all study-required laboratory assessments will be performed at the designated central laboratories.

The time schedule described for weekly assessments should be followed as closely as possible. Allowable time windows are ± 2 days for the weekly assessments through Week 16, ± 7 days for the Week 24 assessment, and $+ 14$ days for the Week 36 follow-up assessment.

A schedule of study assessments/procedures is provided in [Table 5](#).

